13.8.1. Completer (CO) Analysis Set

The CO analysis set will consist of all subjects from the ITT-E analysis set who completed at least the six weeks of treatment and assessments related to the primary endpoint.

### 13.8.2. Per Protocol (PP) Analysis Set

The PP analysis set will consist of all subjects from the ITT-E analysis set without major protocol violations.

#### 13.8.3. Statistical Analysis of Analysis Sets

The ITT-E and ITT-S analysis sets will serve as the main set for efficacy and safety assessments, respectively.

The primary efficacy assessment will also be performed on the CO and the PP analysis sets, as a sensitivity analysis.

### **13.9.** Statistical analysis

# 13.9.1. General Considerations

Statistical analyses will be performed using SAS® v9.4 or higher (SAS Institute, Cary NC, USA). Baseline demographic and other baseline characteristics, together with safety analyses will be performed on all enrolled subjects. Baseline values are defined as the last valid value prior to study treatment. The standard summary statistics for continuous variables are: N, mean, standard deviation, median, minimum and maximum. The standard summary statistics for categorical variables are: count and percentage. All statistical tests will be two-sided. Where confidence limits are appropriate, the confidence level will be 95%. For comparison of means (continuous variables), the two-sample t-test or the Wilcoxon rank sum test will be used as appropriate. For comparison of proportions (discrete data), the Chi-squared test or Fisher's exact test will be used as appropriate.

### 13.9.2. Significance levels and handling of type I error

The overall significance level for this study is 5% using two-tailed tests, except for the treatment by site interaction that will be tested at a significance level of 10%.

The hierarchy approach will be adopted for the primary and secondary endpoints to control the type I error due to multiple endpoint testing. Thus, the primary endpoint will first be analyzed and only if found statistically significant as detailed in section 13.4, will the first secondary endpoint be analyzed; and only if found statistically significant, will the second secondary endpoint be analyzed. This approach will maintain the overall study type I error by continuing to analyze the next end-point in the hierarchy only if the previous endpoint analysis was found significant.

The exploratory end-points will not be part of the hierarchy as descriptive statistics are mainly planned.

#### 13.9.3. Demographic and Other Baseline Characteristics

Demographic and baseline condition related characteristics will be tabulated. Continuous variables such as age and BMI will be summarized by a mean, standard deviation, minimum, median and maximum, and categorical variables by a count and percentage.

### 13.9.4. Disposition of Patients

The numbers of subjects who were randomized and who entered and completed each visit of the study will be provided, as well as the reasons for all post-randomization discontinuations, grouped by treatment and by major reason (e.g., lost to follow-up, adverse event, poor compliance). A list of discontinued subjects, protocol deviations, and subjects excluded from the efficacy analysis will be provided as well. Time to withdrawal will also be assessed and presented by Kaplan-Meier curves and will be compared using the Log-Rank test.

#### 13.9.5. Efficacy analyses

• The continuous quit rate (CQR) at the 6 weeks visit will be compared between the study arms with a chi-squared test. In addition the CQR will be modeled with logistic regression; baseline daily number of cigarettes smoked, sex and center will be used as covariates.

Prognostic factors and sensitivity analysis for the CQR at the 6 week and/or 4 month follow-up visits will be performed in the following manner: adjustment for other covariates such as demographics or other baseline characteristics (e.g., sex, age, race and history of smoking) may be performed by adding these variables to the above described logistic model.

- Weekly point prevalence abstinence rates will be analyzed in the same manner.
- Daily number of cigarettes smoked will be presented over time and analyzed with a repeated measures analysis of covariance model. Baseline daily number of cigarettes smoked, sex and center will be used as covariates.

The analysis will be presented for all subjects in the analysis set and for the non-quitters only.

 Effect on withdrawal symptoms as measured by weekly scales measuring nicotine craving and dependence/withdrawal, including Fagerstrom Test for Nicotine Dependence (FTND), Minnesota Nicotine Withdrawal Scale SelfReport (MNWS), Tobacco Craving Questionnaire–Short Form (TCQ-SF) and Nicotine Craving Scale.

Fagerstrom Test for Nicotine Dependence scores will be presented in tabular form and compared between the treatment arms with chi-squared tests.

Minnesota Nicotine Withdrawal Scale Self-Report scores, Factor structure of Tobacco Craving Questionnaire–Short Form scores, and Nicotine craving scale scores will be presented over time and analyzed with a repeated measures analysis of covariance model. Baseline daily number of cigarettes smoked, sex and center will be used as covariates.

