# 8. RANDOMIZATION AND BLINDING

The subjects will be randomized into the study and stratified by site. If a subject meets the eligibility criteria, he/she will be equally allocated (with a 1:1 ratio) to one of the two (2) treatment groups, based on a stratified randomization scheme random number generator.

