### 13.4. Sample size

The preliminary clinical study evaluated the safety and efficacy of the DTMS as an aid in smoking cessation, at three weeks and at six months follow-up. The three week point prevalence quit rate was 44% in the treatment group and 13% in the sham group. The six month point prevalence quit rate was 33% in the treatment group and 9% in the sham group. Although, the three week point prevalence quit rate showed a significant improvement in the treatment group compared to the sham group, the point prevalence quit rate did not meet the standard requirement for evaluating smoking cessation, i.e., at least a 4 week continuous quit rate. Furthermore, the six month data had its limitations, including a long term time point and high drop-out rate. Therefore, we looked at the clinical results provided in support of FDA approval of other smoking cessation aids, including Zyban (Bupropion hydrochloride) and Chantix (Varenicline). The mechanism of action of Zyban which aids smoking cessation is the increase in dopamine release, which is also one of the mechanisms of action of the DTMS treatment.

The quit rates (i.e., based on abstinence from week 4 of the study through week 7) were 49% in the treatment group receiving Zyban compared to 36% in patients receiving Nicotine Replacement Therapy (NRT) and 23% in the placebo group. In two other studies, subjects treated with Chantix had an abstinence rate during weeks 9 through 12 of 44% compared to 30% in patients treated with Zyban and 17% and 18% in patients receiving placebo.

For the purpose of sample size calculation the weighted average of the quit rates for smoking cessation treatments (including Zyban, Chantix, NRT and DTMS) (38.6%) and the weighted average of the quit rates for placebo/sham (18.4%) will be used. Using the above weighted averages we can assume a placebo/sham success rate of 18%, and a minimally important difference of 20%.

The study is designed to have 80% power with a two-sided level of significance of 5% to detect to detect a difference of 20% in the CQR in the DTMS group compared to the control group, and one planned interim analyses using the Lan De-Mets alpha spending approach with a Pocock type spending function (the calculations were performed using the SAS SEQDESIGN procedure).

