### 13.6. Randomization

A subject meeting the eligibility criteria will be equally allocated (with a 1:1 ratio) to one of the following 2 treatment groups based on a randomization scheme with blocks stratified by center:

- 1. DTMS
- 2. Sham

The randomization scheme will be prepared by the study statistician using the SAS® (version 9.3.) random number procedure. The block size will be variable and study personnel will be blinded to the randomization block size.

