# 13.9.7. Pooling

Subgroup analysis of the primary efficacy endpoint by center will be used to evaluate the poolability of the results. The subject continuous quit status at week 6 by center interaction will be tested with a logistic regression model, using a significance level of 10%. If the interaction is found significant, the reasons for these interactions will be further explored and rationalized. This evaluation may include demographic features, symptoms at presentation, clinical and treatment history, and center comparability in the features found to be associated with the primary efficacy variable. Sites with a small amount of subjects (<10) will be pooled together for this analysis by geographical location.

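### Randomisation is stratified by centre but the main quit-rate test is not: mildly conservative if centres differ, with a small power gain available from a stratified test

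*Protocol*

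**What the plan says.** Protocol section 8 states: "The subjects will be randomized into the study and stratified by site". Section 13.6 repeats this, with 1:1 allocation in blocks of varying size within centre. The synopsis expects approximately 20 sites.

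Section 13.9.5 opens the efficacy analyses with the sentence "The continuous quit rate (CQR) at the 6 weeks visit will be compared between the study arms with a chi-squared test". The next sentence adds: "In addition the CQR will be modeled with logistic regression; baseline daily number of cigarettes smoked, sex and center will be used as covariates". The order and wording make the chi-squared test the main comparison and the centre-adjusted model supplementary. Under 13.9.2 this primary result also gates the secondary endpoints.

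Section 13.9.7 pools sites with fewer than 10 subjects by geography, but only for the poolability analysis. It describes that analysis thus: "The subject continuous quit status at week 6 by center interaction will be tested with a logistic regression model". Section 13.9.2, in its exception to the 5% level, names the same test differently: "except for the treatment by site interaction that will be tested at a significance level of 10" per cent.

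**The concern.** Blocking within centre balances the arms by centre, so differences in quit rate between centres cannot contribute much to the difference between arms. An unstratified test takes no credit for this. It computes its variance as if between-centre variation were still noise in the comparison, so the p-value is somewhat too large whenever centres differ. The protocol itself treats centre as worth adjusting for, since it is a covariate in the logistic and repeated-measures models and has its own poolability section. The test that decides the trial leaves it out.

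At stake is a modest amount of efficiency on the primary endpoint. The interaction wording in 13.9.7 is a separate editorial matter.

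**Working it through.** **1. The plan's own figure.** Section 13.4 assumes "we can assume a placebo/sham success rate of 18%, and a minimally important difference of 20" per cent, with 80% power, two-sided 5% and one interim at about 65% information. The nominal level is 0.03154 at both looks.

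- Unpooled variance: 0.18×0.82 + 0.38×0.62 = 0.1476 + 0.2356 = 0.3832.
- The two-look design needs 1.082 times the fixed-design information: 1.082 × (1.960 + 0.842)² ≈ 8.49.
- Subjects per arm: 8.49 × 0.3832 / 0.20² ≈ 81.4, so 82 per arm and 164 in total, as stated. Power at 164 is 80.3%.

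No centre term enters this calculation. The stated sample size therefore belongs to an unstratified comparison, and test and sample size agree with each other.

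**2. Why the chi-squared test is conservative, and by how much.** Let centre *i* have quit rate p_i, averaging p. The chi-squared test uses the variance p(1−p), which equals the average of p_i(1−p_i) plus Var(p_i). With arms balanced within centre, only the first part belongs to the comparison. The true variance is therefore a fraction 1 − Var(p_i)/[p(1−p)] of the one used, and the effective critical value is 1.96 divided by the square root of that fraction.

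With p = 0.18 under the null, log-odds SDs of 0.5 and 1.0 give SDs of 0.073 and 0.137 on the probability scale.

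- SD 0.5: 0.073²/0.1476 = 0.036; 1.96/√0.964 = 2.00; two-sided error about 4.6%.
- SD 1.0: 0.137²/0.1476 = 0.127; 1.96/√0.873 = 2.10; two-sided error about 3.6%.

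Simulation agrees: 4.5% and 3.7% in one set of runs, 4.7% and 3.5% in another with near-equal centres.

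**3. What the assumed SDs mean.** Around a typical centre at 18% (log-odds −1.516), one SD either side covers about 12% to 27% at SD 0.5 and about 7% to 37% at SD 1.0. The second is a strong assumption.

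**4. Power at the design effect.** Simulated trials, 164 subjects, 18% against 38%, single look at two-sided 5%, CMH test with centres under 10 pooled:

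| Between-centre SD (assumed) | Chi-squared | CMH, small centres pooled | Gain |
|---|---|---|---|
| 0 | 82.6% | 82.6% | 0 |
| 0.5 | 84.1% | 84.6% | 0.5 |
| 1.0 | 84.2% | 86.4% | 2.2 |

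A separate run, with 11 centres under 10 subjects, gave 83.2% against 83.9–84.0% at SD 0.5, and 84.1% against 86.3–86.5% at SD 1.0.

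Without pooling (20 near-equal sites), CMH changes power from 82.2% to 82.0% at SD 0, from 83.0% to 83.9% at SD 0.5, and from 84.2% to 87.6% at SD 1.0. Pooling therefore gives back part of the gain. At the 3.154% level the unpooled figures are 77.5% to 78.7% (SD 0.5) and 78.7% to 83.3% (SD 1.0). These lie lower because of the stricter level at a single look: the chi-squared figure with no centre differences is already 76.8%.

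With 270 evaluable, the largest unpooled gain at 5% is 96.6% to 97.6% (SD 1.0).

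**5. The supplementary model.** 164/20 = 8.2 subjects per site on average, below the protocol's own threshold of 10. Expected quitters are 82 × (0.18 + 0.38) ≈ 46, or 135 × 0.56 ≈ 76 at 270 subjects, against about 20 centre terms. At an average rate of 28%, a site of 8 has no quitters with probability 0.72⁸ ≈ 7%. Some centre terms would be sparse unless the pooling rule is extended to this model.

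**6. The interaction wording.** Section 13.9.7 crosses quit status with centre, and quit status is the outcome. Section 13.9.2 crosses treatment with site, also at 10%. Only the second describes a test of whether the treatment effect varies by centre.

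**The case against.** The strongest reply is that nothing here threatens the trial's conclusion. The error is on the safe side, the sample size was computed for the test the plan names, and the plan already includes a centre-adjusted model. All of that stands.

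A reader might go further than the document allows in four ways.

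- *The plan is underpowered because it ignores centre.* It is not. With the marginal rates held at 18% and 38%, chi-squared power did not fall below its value with no centre differences (82.2% at SD 0, 84.2% at SD 1.0). The loss is only relative to a stratified test.
- *The test always loses power.* The effect depends wholly on between-centre variation, which the protocol does not quantify. With none, nothing is lost.
- *The logistic model will break down on small centres.* A centre with no quitters has a divergent centre term but adds nothing to the treatment coefficient, and it adds nothing to a CMH test either. Pooling in a supplementary model is also ordinary detail for a statistical analysis plan, which was not available.
- *The poolability analysis will use the outcome as its own predictor.* Section 13.9.2 names the intended test correctly, and 13.9.7 is introduced as a check of the primary endpoint by centre. This is a drafting slip.

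The reply also notes that the trial looks well advanced: section 13.4 describes dropout monitoring in the past tense, and the heading of 13.5 says the interim was not performed. Changing the primary test at that stage is a substantive amendment, acceptable only while the data remain blinded.

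**Conclusion.** The mismatch between stratified allocation and an unstratified main test is real and worth correcting, but it is a small matter of efficiency. If centres differ, the chi-squared test runs at about 4.5% (SD 0.5) to 3.7% (SD 1.0) in place of 5%. A centre-stratified test with small centres pooled would gain under 1 point of power at SD 0.5 and about 2 points at SD 1.0. There is no gain or material loss if centres are alike, and at most about 1 point is gained with 270 evaluable.

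These sizes rest on assumed between-centre SDs, about 20 centres, close balance within centre, the design rates of 18% and 38%, and a single look at two-sided 5%. Validity is not in question and the stated 80% power stands. The interaction wording is editorial and adds no weight to the main point.

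**What to change.** Before unblinding, and by dated amendment or in the statistical analysis plan:

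1. Make a CMH test stratified by centre the primary comparison of the four-week quit rate, with centres of fewer than 10 subjects pooled by the rule already in 13.9.7.
2. Use the same pooled centres in the logistic model of 13.9.5.
3. Keep the plain chi-squared test as a sensitivity analysis.
4. In 13.9.7, name the interaction as treatment by centre, to match 13.9.2.

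No new data, subjects or visits are needed. The cost is a formal change to the primary test, so the date and the blinded status of the data should be documented. Item 4 is wording only. If the data have already been unblinded, the chi-squared test should stay primary and the stratified test be reported as supportive.

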### 1. STUDY SYNOPSIS

**Name of Device:** Brainsway Deep Transcranial Magnetic Stimulation (DTMS) device (H-ADD Coil).

**Device Description:** The Brainsway DTMS device is intended as an aid to smoking cessation. The device technology is based on the application of Deep TMS by means of repetitive pulse trains at a determined frequency.

**Objectives:** The aim of the study is to evaluate the safety and efficacy of DTMS compared to sham treatment as an aid to smoking cessation in chronic ( $\geq 10$  cigarettes/day) cigarette smokers.

**Patient Population:** The intention is to enroll a minimum of 224 subjects. The subjects will be of all racial, ethnic and gender categories, ranging from 22 to 70 years of age. Patients will be recruited from both academic and private research centers.

**Structure:** The study is a randomized, prospective, 4 month, double blind, multicenter study (see study flow chart in Attachment 1).

**Blinding:** The treatment administrator, study rater, all study personnel and subjects will be masked to the treatment being administrated.

**Concurrent Control:** The study group will receive active DTMS treatment and the control group will receive inactive, sham treatment.

**Sample Size:** A maximum of 270 subjects (135 in each treatment group) from approximately 20 sites will be enrolled in the study.

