### 13.4.4. Alpha level

The study is designed as a group sequential study with one planned interim analysis with a Pocock type spending function using the Lan De-Mets alpha spending approach. The study hypothesis will be tested at the time of the interim analysis. If the 2-sided p-value of the comparison of the primary endpoint (CQR) between the two study arms is statistically significant, i.e. <0.03154, the study will be stopped and considered successful. Otherwise, the primary endpoint will be tested at the end of the planned study for a level of significance of 3.154%.

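### The supportive adjusted quit-rate model enters about 20 small centres as covariates, which overstates a true log odds ratio by about 10–12% at 270 subjects

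*Protocol*

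**What the plan says.** Section 13.9.5 makes the main comparison unadjusted: "The continuous quit rate (CQR) at the 6 weeks visit will be compared between the study arms with a chi-squared test". It then adds the model at issue: "In addition the CQR will be modeled with logistic regression; baseline daily number of cigarettes smoked, sex and center will be used as covariates". Weekly point prevalence abstinence is to be analysed the same way. Sensitivity models may add further baseline variables to the same logistic model.

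The synopsis gives the scale: "A maximum of 270 subjects (135 in each treatment group) from approximately 20 sites will be enrolled in the study", and also "The intention is to enroll a minimum of 224 subjects". Section 13.4 requires 164 evaluable subjects and allows for 37% drop-out. Section 13.9.8 counts drop-outs as non-abstinent.

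The only rule for small sites is in section 13.9.7, which tests the interaction with centre: "Sites with a small amount of subjects (<10) will be pooled together for this analysis by geographical location". Section 13.9.5 has no such clause. Section 13.6 randomises in blocks within centre.

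**The concern.** Maximum-likelihood logistic regression with a separate parameter for each small centre is biased away from the null, because the number of nuisance parameters is large relative to the data in each centre. The protocol names both the model and its covariates, and its small-site protection applies elsewhere. An analysis that follows 13.9.5 literally would inherit the bias.

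This model is the only specified adjusted estimate of the primary effect, and it is also the base for the weekly-abstinence and sensitivity models. If the device works, the adjusted odds ratio would look stronger than it is, and could look better than the chi-squared result for reasons unrelated to efficacy.

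**Working it through.** **Inputs from the protocol.** About 20 sites; 224 to 270 enrolled; 164 evaluable; quit rates 18% and 38% (section 13.4: "we can assume a placebo/sham success rate of 18%, and a minimally important difference of 20" per cent); 37% drop-out; 1:1 blocks within centre.

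**Assumptions, not in the protocol.** Centre sizes (equal and uneven were both tried) and the between-centre standard deviation on the logit scale (0.3 or 0.5 in the results below; results change little over 0 to 0.8).

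**The plan's own figure.** The protocol gives no performance figure for this model. Its sample size does reproduce: two looks at 65% and 100% information, p<0.03154 at each, 80% power and unpooled variance give 162.7, hence 82 per arm and 164 in total.

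**Sparsity.**
- Subjects per site: 270/20 = 13.5; 224/20 = 11.2; 164/20 = 8.2.
- Slope parameters: 19 centre terms + arm + sex + baseline cigarettes = 22.
- Expected quitters at an average rate of (0.18 + 0.38)/2 = 0.28: 270 × 0.28 = 75.6 and 164 × 0.28 = 45.9. That is 3.4 and 2.1 per parameter.
- With drop-outs as failures, the rates become 0.63 × 18% = 11.3% and 0.63 × 38% = 23.9%. At 270 subjects this gives about 48 quitters, or 2.2 per parameter.

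**Model simulated.** logit P(quit) = centre term + β·arm + γ·sex + δ·baseline cigarettes. The yardstick is the within-centre odds ratio, so the gap is not ordinary non-collapsibility. At 18% versus 38% with both covariates, the true within-centre odds ratio is 2.98.

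| N | Method | Median OR | Mean log OR bias | 95% CI coverage | Null Wald size |
|---|---|---|---|---|---|
| 270 | centre indicators | 3.33 | +10.5% | 93.1% | 5.7% |
| 164 | centre indicators | 3.66 | +20% | 90.8% | 6.6% |
| 270 | conditional on centre, both covariates | 3.03 | see below | about 95% | 5.1–5.2% |
| 164 | conditional on centre, both covariates | 3.12 | see below | about 95% | 5.1–5.2% |

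On the medians, the conditional fit leaves ln 3.03/ln 2.98 = 1.109/1.092, or +1.5%, and ln 3.12/ln 2.98 = 1.138/1.092, or +4.2%.

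**Replication.**
- A separate simulation with uneven centres gave a median OR of 3.31 at 270 (log OR +10%, coverage 92.9%) and 3.52 at 164 (+17%, 92.2%). Null size was 6.1–6.6% for the Wald test and 6.5–7.0% for the likelihood-ratio test.
- With drop-outs as failures at 270, the log OR bias was +11% in one run and +12% in another.
- A third simulation had centre indicators only, standard deviation 0.3 and a true OR of 2.84. The fitted OR was too high by factors of 1.102 (N = 270), 1.125 (224) and 1.181 (170). On the log scale: ln 1.102/ln 2.84 = 0.097/1.044 = +9.3%; 0.118/1.044 = +11.3%; 0.166/1.044 = +15.9%.
- Across nearly all 20-centre settings of that re-derivation, null size was 5.8–7.0% (Wald) and 6.1–7.5% (likelihood ratio). The lowest was 5.2% and 5.5%, at 270 with an 18% quit rate and no other covariates. The chi-squared test stayed at 4.4–5.7%.

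**The case against.** **It decides nothing.** Success rests on the chi-squared comparison; section 13.4.4 states that "the primary endpoint will be tested at the end of the planned study for a level of significance of 3.154" per cent applies to the primary endpoint. The logistic p-value has no decision role, and weekly abstinence is exploratory and outside the hierarchy. This stands and limits the point to a supportive estimate.

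**Centre coding belongs in the SAP.** A SAP could condition on centre, pool sites or use another fit. That possibility is real. But the protocol names the model and lists centre among its covariates, so this is a stated method that performs badly rather than an omitted detail.

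**The pooling rule might be carried over.** If sites under 10 were also pooled here, simulated log OR bias fell to between +5% and +9% at 164, but only to +8% or +9% at 270, where most sites exceed 10. One of those runs gave a Wald size of 4.9–5.1%. The text ties the rule to the interaction analysis, and much of the bias at 270 remains even if it is extended.

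**The larger figures use a small N.** This stands. The primary denominator in section 13.2.1 is subjects treated with at least one post-baseline assessment, with drop-outs counted as failures. An analysed N near 164 is closer to the completer set, so 10–12% is the main figure.

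**Enrolment may concentrate.** With only 10 effective centres the odds ratio is inflated by 7–12% and Wald size is 5.4–6.5%. The problem is smaller but does not vanish.

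**Conclusion.** The point holds for the supportive adjusted analysis. Near the planned effect, the model as written overstates the log odds ratio by about 10–12% at 270 subjects, and by up to about 17–20% if only about 164 are analysed. Interval coverage is about 91–93%, and a nominal 5% test runs at about 6–7%. This rests on the plain reading of centre as a covariate, about 20 unpooled sites, and assumed centre sizes and spread.

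A reader might infer more, but the documents and the check do not support it:
- *That the primary claim is compromised.* It rests on the chi-squared test, whose size is sound.
- *That the model could create a device effect.* With equal quit rates the fitted odds ratio centres on about 1.00; the cost there is about 1–2 points of test size.
- *That the intervals are simply too narrow.* Much of the under-coverage comes from the shifted estimate. At 270 the standard error was larger with centre indicators than with conditioning (0.315 versus 0.303).
- *That centres without quitters invalidate the fit.* They add nothing to the arm estimate under either method.

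**What to change.** In section 13.9.5, replace centre as a covariate in the CQR and weekly-abstinence logistic models by conditional logistic regression stratified by centre, with arm, baseline daily cigarettes and sex as covariates. Build the sensitivity models that add baseline variables on the same stratified model. This matches randomisation within centre and brings the log odds ratio bias down to about 2–5%, with coverage of about 95% and size of about 5%.

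The cost is one line of wording and one of code. Centre effects are no longer estimated, and the adjusted odds ratio becomes slightly less favourable. The chi-squared test, the sample size and the data collected do not change.

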# 13.2.2. Secondary Efficacy Endpoints

The secondary endpoints are:

- The four-week continuous quit rate (CQR), representing abstinence during a consecutive 4 week period for subjects having assessments during a consecutive 4 weeks period, therefore the quit rates are defined as the ratio of the number of patients meeting the quit criterion for at least 4 consecutive weeks to the total number of patients having assessments during a consecutive 4 week period.
- The number of cigarettes smoked per day (per diary data) for all subjects (quitters and non-quitters).

13.2.3. Exploratory Efficacy Endpoints Additional endpoints include:

- Weekly point prevalence abstinence rates, defined as the ratio of the number of subjects meeting the weekly abstinence criterion to the number of subjects initially treated and having at least one post-baseline assessment.
- Number of cigarettes smoked per day (per diary data) for non-quitter subjects only.
- Withdrawal symptoms as measured by weekly scales measuring nicotine craving and dependence/withdrawal, including the Fagerstrom Test for Nicotine Dependence (FTND), Minnesota Nicotine Withdrawal Scale Self-Report (MNWS), Tobacco Craving Questionnaire–Short Form (TCQ-SF) and Nicotine Craving Scale.

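### Section 13.9.5 compares cigarettes per day between arms in non-quitters only, an exploratory and non-randomised comparison that should be shown descriptively without a model or test

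*Protocol*

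**What the plan says.** Section 13.9.5 sets the model: "Daily number of cigarettes smoked will be presented over time and analyzed with a repeated measures analysis of covariance model". The covariates are baseline daily cigarettes, sex and center. The next sentence extends the analysis to a subset: "The analysis will be presented for all subjects in the analysis set and for the non-quitters only".

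The two versions have different rank.

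- **All subjects.** This is the second of the two secondary endpoints in section 13.2.2. Section 13.9.2 places it in the fixed testing order.
- **Non-quitters.** Section 13.2.3 lists it as exploratory: "Number of cigarettes smoked per day (per diary data) for non-quitter subjects only". The Synopsis and section 5.3 do the same. Section 13.9.2 adds: "The exploratory end-points will not be part of the hierarchy as descriptive statistics are mainly planned".

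The planning quit rates are in section 13.4: "Using the above weighted averages we can assume a placebo/sham success rate of 18%, and a minimally important difference of 20" (percentage points), which implies 38% on active. Section 13.9.8 counts dropouts as non-abstinent.

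**The concern.** The non-quitter analysis appears to ask whether DTMS lowers consumption in people who go on smoking. Whether a subject goes on smoking is decided after randomisation, by the outcome the device is meant to change. If the device works as planned, it takes more subjects out of the active non-quitter set than sham treatment takes out of the sham set. The two remaining groups then differ in how hard their members find it to quit, even if DTMS changes nobody's consumption.

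Baseline cigarettes, sex and center are measured before the quit attempt. They adjust for what was known at entry, not for selection on the response to that attempt.

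At stake is the meaning of a model estimate and p-value that the protocol asks for. In a successful trial they could suggest that DTMS non-quitters smoke more than sham non-quitters, or they could understate a real reduction.

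**Working it through.** **Inputs from the protocol.** Quit rates 18% and 38%, 80% power, two-sided 5%, 82 per arm required, 270 randomised (135 per arm) to allow for 37% drop-out (section 13.4); nominal level 0.03154 at each look (section 13.4.4 under Interim Analysis).

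**The plan's own figure.** A two-look design at 65% information, with 0.03154 two-sided at both looks, 80% power, 18% v 38% and unpooled variance gives 81.4, so 82 per arm and 164 in total. The stated figure reproduces.

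**Assumption not in the protocol.** ρ is the correlation between difficulty of quitting (U, standard normal) and later cigarettes per day after baseline adjustment (SD 1). The range shown is 0.3 to 0.7. A subject quits if U falls below the 38th percentile (active) or the 18th (sham).

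**Step 1, size of the sets.** Non-quitters are 62% of active and 82% of sham. With 82 per arm that is 0.62 × 82 = 51 and 0.82 × 82 = 67. With 135 per arm it is 84 and 111.

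**Step 2, selection gap.** The mean of U above the cut-off is φ(z)/(1 − p).

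- Active: z = −0.3055, 0.3808/0.62 = 0.614.
- Sham: z = −0.9154, 0.2624/0.82 = 0.320.
- Gap: 0.614 − 0.320 = 0.294 SD.

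**Step 3, bias and false rejection with no effect on consumption.** Bias = ρ × 0.294. SE = √(v₁/n₁ + v₀/n₀), where v = 1 − ρ² + ρ² × (variance of U above the cut-off). That variance is 0.435 on active and 0.605 on sham. For ρ = 0.5 and 82 per arm, v₁ = 0.75 + 0.25 × 0.435 = 0.859 and v₀ = 0.75 + 0.25 × 0.605 = 0.901. So SE = √(0.859/50.8 + 0.901/67.2) = 0.174, and bias/SE = 0.147/0.174 = 0.85. The chance of exceeding the critical value of about 1.98 in either direction is then about 13%.

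| ρ | bias (SD) | bias/SE, 82 per arm | rejects | bias/SE, 135 per arm | rejects |
|---|---|---|---|---|---|
| 0 | 0 | 0 | 5% | 0 | 5% |
| 0.3 | 0.09 | 0.49 | 7% | 0.62 | 9% |
| 0.5 | 0.15 | 0.85 | 13% | 1.08 | 19% |
| 0.7 | 0.21 | 1.27 | 24% | 1.63 | 37% |

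Simulations of the same set-up agree within about 2 points, reaching 26% at ρ = 0.7 with 82 per arm. Nearly all rejections say that active smokes more. With equal quit rates, rejection stays near 5%, so the selection is the cause.

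**Step 4, a true reduction in continuing smokers.** Expected estimate = −effect + bias, at ρ = 0.3, 0.5 and 0.7.

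- True 0.15 SD: −0.06, about 0, +0.06.
- True 0.30 SD: −0.21, −0.15, −0.09. Power at 82 per arm falls from 37% at ρ = 0 to 21%, 13% and 8%.
- True 0.40 SD: −0.31, −0.25, −0.19.

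**Step 5, what moves the result.**

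- A negative ρ turns the bias in favour of active: −0.09 SD at −0.3 and about −0.15 at −0.5.
- Near-quitters who miss the four-week criterion may still contribute zero-cigarette weeks. In a simulation in cigarettes (between-subject SD of 5 assumed, 82 per arm), this cut the bias from 0.42 to 0.10 per day at ρ = 0.3, and from 0.71 to 0.37 at ρ = 0.5.

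**The case against.** The strongest reply is that little depends on this analysis. It is exploratory, outside the hierarchy, and covered by a statement that exploratory endpoints are mainly descriptive. The randomised comparison of consumption in all subjects is already planned and is the one formally tested. All of that stands, and it limits the weight of the point. It does not remove it: section 13.9.2 says mainly, not only, and section 13.9.5 puts the non-quitter set under the model. Lying outside the hierarchy answers multiplicity, not bias.

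A second reply is that the size rests on a correlation the protocol does not give, and that 135 per arm with undiluted quit rates is the high end. This also stands. The rates of 18% and 38% belong to the 82 per arm. If all 135 are kept and dropouts count as non-abstinent, the quit rates become about 0.38 × 82/135 = 23% and 0.18 × 82/135 = 11%. The gap falls to about 0.19 SD, and rejection with 135 per arm to about 7%, 11% and 20% at ρ = 0.3, 0.5 and 0.7. The bias is smaller but still there.

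A reader might also infer that the test will reject whenever more subjects quit on active, or that it reverses a real benefit. The figures do not support either. Rejection is a minority outcome throughout, and reversal on average appears only for a small effect (about 0.15 SD) at the strongest correlation. Effects of 0.30 or 0.40 SD are shrunk but keep their direction.

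**Conclusion.** The point holds as a flaw in an exploratory analysis. Section 13.9.5 prescribes a between-arm model in a set defined by the primary outcome, and the listed covariates cannot restore comparability. Under a correlation of 0.3 to 0.7, the contrast is shifted against active by about 0.09 to 0.21 SD. With no effect on consumption, the nominal 5% test rejects in about 7% to 26% of trials at 82 per arm (9% to 37% at 135).

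Those figures assume a sharp quitting threshold and the planning quit rates. Neither the size nor the sign of the bias can be fixed from the protocol, so the estimate cannot be read safely in either direction.

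It would go too far to conclude that the trial's error control is affected or that consumption lacks a valid analysis. The primary endpoint and the hierarchy are untouched, and the all-subjects comparison is in place.

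**What to change.** In section 13.9.5:

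- Restrict the repeated-measures model and the between-arm test of cigarettes per day to all subjects in the analysis set.
- Show cigarettes per day in non-quitters by arm with descriptive statistics only, labelled as a non-randomised comparison. This brings the section into line with section 13.9.2.
- State that any conclusion about treatment effect on consumption rests on the all-subjects secondary endpoint in section 13.2.2.

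No new responder endpoint is needed. One that counted quitters as reducers would be driven partly by quitting and would not answer the question about continuing smokers.

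The cost is a change of wording, with no new data. The sponsor gives up an exploratory p-value and model estimate in non-quitters.
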